9.5.4 Safety Assessments

9.5.4.1 Adverse Events

An AE is any untoward medical occurrence in a patient or clinical investigation subject administered a pharmaceutical product and which does not necessarily have to have a causal relationship with this treatment. An AE can therefore be any unfavorable and unintended sign (including an abnormal laboratory finding, for example), symptom, or disease temporally associated with the use of a medicinal product, whether or not considered related to the medicinal product (ICH-E2A).

For the purpose of the site's data collection responsibilities, any untoward event that was reported from the time the patient signed the ICF until 30 days after the last known dose of investigational product, until ADA positive status for antibody positive patients has reverted to ADA negative, or until the end of the Follow-up Period (whichever is later), is to be considered an AE.

Examples of AEs are as follows:

- Changes in the general condition of the patient
- Subjective symptoms offered by or elicited from the patient
- Objective signs observed by the Investigator or other study site personnel
- All diseases that occur after signing informed consent, including any change in severity or frequency of pre-existing disease
- All clinically relevant abnormalities in laboratory values or clinically relevant physical findings that occur during the study schedule

Please note that medical procedures scheduled prior to consenting, but occurring during the study should not be captured as AEs, but should be listed in the medical history if related to a pre-existing condition.

9.5.4.3 Severity Assessment

The Investigator will provide an assessment of the severity of each AE by recording a severity rating on the appropriate AE reporting page of the patient's eCRF. *Severity*, which is a description of the intensity of manifestation of the AE, is distinct from *seriousness*, which implies a patient outcome or AE-required treatment measure associated with a threat to life or functionality (Section 9.5.4.4). Severity will be assessed according to the following scale:

- Mild:** The AE was an annoyance to the patient but did not further hinder baseline functioning; the AE may have been intermittent or continuous.
- Moderate:** The AE caused the patient to experience some discomfort or some interference with normal activities but was not hazardous to health; prescription drug therapy may have been employed to treat the AE.
- Severe:** The AE caused the patient to experience severe discomfort or severely limited or prevented normal activities and represented a definite hazard to health; prescription drug therapy and/or hospitalization may have been employed to treat the AE.

9.5.4.4 Serious Adverse Events

An SAE is any untoward medical occurrence that at any dose:

- Results in death
- Is life threatening
- Requires inpatient hospitalization or prolongation of existing hospitalization
- Results in a persistent or significant incapacity or substantial disruption of the ability to conduct normal life functions, or
- Is a congenital anomaly/birth defect

Important medical events that may not result in death, be life threatening, or require hospitalization may be considered serious when, based on appropriate medical judgment, they may jeopardize the patient or subject and may require medical or surgical intervention to prevent one of the outcomes listed in this definition. Examples of such medical events include allergic bronchospasm requiring intensive treatment in an emergency room or at home, blood dyscrasias or convulsions that do not result in patient hospitalization, or the development of investigational product dependency or drug abuse.

Emergency room visits that do not result in hospitalization should be evaluated for one of the other serious outcomes to determine whether they qualify as SAEs.

Preplanned hospitalizations (eg, elective procedures for pre-existing conditions that did not worsen, such as cosmetic surgery and hysterectomy) are excluded from SAE reporting.

9.5.4.5 Reporting Adverse Events and Serious Adverse Events

At each visit, patients are to be queried regarding any AEs or SAEs that have occurred since the previous visit. Patients will be asked to volunteer information with a nonleading question such as, “How do you feel since your last visit?” Study site personnel will record all pertinent information in the patient’s eCRF. Any AEs reported in diaries will also be reported on the relevant eCRF page.

All AEs must be recorded on the appropriate AE reporting page of the patient’s eCRF whether or not they are considered causally related to the investigational product.

For every AE, the Investigator must:

- Provide an assessment of the seriousness of the event (ie, is it an SAE?), as well as the severity and causal relationship
- Document all actions taken with regard to the investigational product
- Detail any other treatment measures taken for the AE
- Document the outcome of the AE

In addition, patients are to be reminded, as described in the ICF and in accordance with Section 9.5.4.1, to notify site personnel of any AEs occurring up to 30 days after the last known dose of linaclotide, or for ADA positive patients, until the end of the 8-month Follow-up Period. Any AEs reported by the patient (or patient representative) during this period are to be recorded in original source documents. AEs are also to be recorded in the eCRF if at least 1 of the following conditions is met: 1) the event meets the criteria for an SAE (see Sections 9.5.4.4 and 9.5.4.6), and/or 2) the event is considered by the Investigator to be potentially causally related to investigational product.

Any AEs that are ongoing at the time of the final protocol-defined study visit will be followed until the condition returns to prestudy status, has resolved or stabilized, or can be explained as being unrelated to the investigational product. If a follow-up visit is deemed necessary for appropriate safety surveillance, it will take place within 30 days of the final protocol-defined study visit.

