The follow-up period consists of a 1-month telephone visit for all patients (Visit 9). A 4-Month Follow-Up Visit (Visit 10) is required only for patients with treatment-related ADAs at the time of study completion (52 weeks, Visit 8) or early termination [ET]. If treatment-related ADAs are still present in the patient's serum at the 4-Month Follow-up Visit, an 8-Month Follow-up Visit will be required for ADA testing. Patients completing the 4-Month Follow-up Visit will also have a subsequent 1-month telephone call to review ADA status and determine if continuation to an 8-Month Follow-up Visit (Visit 11) is necessary.

If an ADA-positive patient becomes ADA negative or a baseline ADA-positive patient's titer returns to less than 4-fold the baseline titer at the end the treatment period (52 weeks or early termination) or 4-Month Follow-up Visit (Visit 10), no further follow-up or visits are required. A list of assessments and the visits at which they are performed is provided in the Schedule of Evaluations (Section 2.0).

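### Does Protocol 9.5.4.5 leave open whether a non-serious, unrelated adverse event reported after the last dose belongs in the eCRF?

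*Protocol*

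**What the plan says.** Protocol 9.5.4.5 opens with the visit routine: "At each visit, patients are to be queried regarding any AEs or SAEs that have occurred since the previous visit", with staff entering the information in the eCRF. The next sentence is general. Every AE goes on the AE page of the "eCRF whether or not they are considered causally related to the investigational product". Neither sentence states a time limit.

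A later paragraph of the same section covers the time after treatment. Patients are reminded to report events for 30 days after the last known dose, "or for ADA positive patients, until the end of the 8-month Follow-up Period". For such reports it says: "Any AEs reported by the patient (or patient representative) during this period are to be recorded in original source documents". It continues: "AEs are also to be recorded in the eCRF if at least 1 of the following conditions is met", namely that the event is serious or that the investigator judges it potentially related to the product.

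Protocol 9.5.4.1 sets the collection window, which starts at consent: "data collection responsibilities, any untoward event that was reported from the time the patient signed the ICF until 30 days after". Those 30 days are counted from the final dose. The window then extends "until ADA positive status for antibody positive patients has reverted to ADA negative, or until the end of the Follow-up Period (whichever is later").

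Protocol 9.1 (Follow-up Period) describes the visits after treatment: "The follow-up period consists of a 1-month telephone visit for all patients (Visit 9"). Visits 10 and 11, at 4 and 8 months, are only for patients whose treatment-related ADAs persist.

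SAP Table 5-20 counts an event as treatment-emergent if it starts no later than 1 day after the treatment end date. It calls an event on-therapy if it starts no later than 30 days after that date.

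**The concern.** Two sentences in one section appear to give different instructions for the same event. The general sentence would put a mild, unrelated event reported two weeks after the last dose into the database. The post-dose paragraph would leave it in the source notes. No sentence says outright that the second limits the first, and the 1-month call is itself labelled a visit. An event elicited there can therefore be read under either rule, and two careful sites could act differently.

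Three things make this worth checking:

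- Protocol 7.5 says that AE collection is part of the post-marketing requirement, and that antibody findings should be related to clinical outcomes.
- Under the narrower rule the investigator's causality judgement decides database entry. Protocol 9.5.1.1 has investigators told the ADA status before the 1-month call, so entry could in principle depend on it.
- Sections 9.5.4.1 and 9.5.4.5 word the end of collection for ADA-positive patients differently. It is not obvious how either applies to someone who reverts at 4 months and needs no 8-month visit.

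**Working it through.** The plan states no figure on this point. The check is mainly a reading of the text, with simple arithmetic on the time windows.

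**1. Apply the post-dose rule to every case.** The conditions are serious (S) and potentially related (R); entry is required if at least one holds.

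| S | R | Conditions met | Source documents | eCRF entry required |
|---|---|---|---|---|
| yes | yes | 2 | yes | yes |
| yes | no | 1 | yes | yes |
| no | yes | 1 | yes | yes |
| no | no | 0 | yes | no |

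All four cases have an answer, so the instruction is not missing.

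**2. Which rule governs after the last dose?** The post-dose paragraph states its own period and refers back to it. If every post-dose event already had to be entered, its two conditions would have no function. The ordinary reading is that the specific rule limits the general one. A site that enters everything breaks neither sentence, so the worst outcome is uneven entry of the last row of the table.

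**3. How much of the analysis can this touch?** Let T be days on treatment.

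- Treatment-emergent window: T + 1 days, of which 1 is post-dose. For a 52-week completer T = 364, so 1/365 = 0.3%. For a patient assumed to stop at 2 weeks T = 14, so 1/15 = 6.7%.
- On-therapy window: T + 30 days, of which 30 are post-dose and 30 − 1 = 29 lie outside the treatment-emergent window. For T = 364, 30/394 = 7.6%; for T = 14, 30/44 = 68.2%.

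These are shares of calendar time, not of lost events. Within them only non-serious, unrelated events could be affected. Their number lies between none (all sites enter everything) and all of them (all sites apply the conditions). The documents give nothing to narrow that range.

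**4. End of the window for a patient who reverts at 4 months.** Section 9.5.4.5 names the 8-month period. Section 9.5.4.1 can be read in three ways:

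- the same 8-month period: 8 − 8 = 0 months' difference;
- follow-up ends at the telephone call 1 month after the 4-month visit: 8 − 5 = about 3 months;
- follow-up ends at the 4-month visit: 8 − 4 = about 4 months.

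Section 9.5.4.5 says its reminder accords with 9.5.4.1. The 8-month phrase is what patients are told; 9.5.4.1 defines what the site collects. On that reading, a patient who reports beyond the collection window supplies more than is needed.

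**5. Could ADA status distort a comparison?** After the 1-month call, only patients with treatment-related ADAs at the end of treatment are scheduled to return. There is then no scheduled ADA-negative group to compare with. At the call itself both groups are contacted, so differential entry is possible there, but only for events judged both non-serious and unrelated. A suspected antibody-related reaction would be judged potentially related, and so entered.

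**The case for a change.** The strongest case on the other side is textual. The general sentence is mandatory and has no time limit. The post-dose paragraph is introduced as an addition, not an exception, and it says if, not only if. Preferring the specific rule is thus an inference. Protocol 9.4.8 also counts Visits 9 to 11 among study visits, so a non-serious, unrelated event mentioned at the 1-month call falls under the visit query and the post-dose paragraph alike. Removing the conditions would cost little, because the events are already in source documents, and it would take the causality judgement out of the decision to enter.

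Part of this stands. A clause saying which rule covers Visits 9 to 11, and one shared definition of the end of the window, would read better. But these are matters of wording. Removing the conditions is another matter: limiting post-dose eCRF entry to serious or potentially related events is a data-collection choice open to the sponsor, and the visible plan shows no analysis that suffers from it.

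Protocol 9.5.4.2, the Schedule of Evaluations and much of the SAP safety section are not visible. They may clarify the point or use the on-therapy term, so their absence supports neither side.

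**Conclusion.** The concern does not hold as a reason to change the plan. The protocol does say what to do with a non-serious, unrelated event reported after the last dose: record it in source documents, with no eCRF entry required. What is left is an overlap between a general and a specific sentence, most noticeable at the 1-month call, and two wordings for the end of follow-up that differ by 0, about 3 or about 4 months for one type of patient.

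The consequence is small as far as it can be seen. Serious events, potentially related events and the primary ADA endpoint are untouched. Treatment-emergent summaries are exposed through a single post-dose day. The on-therapy term is exposed for 30 days, but no visible table is built on it. The number of events is unknown.

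This rests on two assumptions: that sites read the specific post-dose rule as governing its own period, and that the unseen safety tables do not rely on complete entry of non-serious, unrelated events after the last dose. If such a table existed, the wording would deserve a second look.

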9.5.4.6 Immediate Reporting of Serious Adverse Events

The Sponsor is required to inform worldwide regulatory authorities of SAEs that meet specific criteria. Therefore, the Sponsor must be notified immediately regarding any SAE that occurs after informed consent is obtained.

Within 24 hours of learning of any AE that meets one of the criteria for an SAE, the study site personnel must report the event to Forest Patient Safety on the SAE Form for Clinical Studies. The Sponsor's Study Physician may also be notified by telephone.

If, during follow-up, any nonserious AE worsens and eventually meets the criteria for an SAE, that AE should be recorded as a new SAE.

The site must transmit the SAE Form for Clinical Studies to the SAE fax number shown below. Even if an initial report is made by telephone, the SAE Form for Clinical Studies completed with all available details must still be faxed within 24 hours of knowledge of the event at the study site.

Supplemental information should be submitted as soon as available and may include laboratory results, radiology reports, progress notes, hospital admission and emergency room notes, holding and observation notes, discharge summaries, autopsy reports, and death certificates.

The Investigator is expected to take all therapeutic measures necessary for resolution of the SAE. Any medications or procedures necessary for treatment of the SAE must be recorded on the appropriate pages of the patient's eCRF. All SAEs are to be followed by the study staff until resolution or until the SAE is deemed stable. ***The Sponsor may contact the study site to solicit additional information or follow up on the event.***

Fax the SAE Form for Clinical Studies to Forest Research Institute, Inc.

SAE fax number: [REDACTED]

Sponsor's Study Physician Medical Emergency phone number: [REDACTED]

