5.1.1.4.2 Adverse Events

[figure not shown]
The following adverse event (AE) terms are defined:

Table 5–20 AE Terms

Term	Description			
Treatment-	An event that meets the following condition:			
emergent	 Treatment start date ≤ event start date ≤ treatment end date + 1 and meets either of the following conditions: 			
	 The same term is never reported before the treatment start date 			
	• The same term is reported before the treatment start date and the term increases in severity on or after the treatment start date			
	 Event severity > maximum severity of same term reported before the treatment start date 			
On-therapy	An event where:			
	• Treatment start date ≤ event start date ≤ treatment end date + 30			

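### The SAP's treatment-emergent rule tests worsening by severity grade alone, so an AE that begins in screening and becomes serious on treatment without a higher grade is not counted as treatment-emergent

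*Protocol*

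**What the plan says.** AE collection starts at consent (Protocol 9.5.4.1), and screening lasts up to 21 calendar days (Protocol 9.1), so some AE records predate the first dose.

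**Recording (protocol).** Section 9.5.4.3 states: "The Investigator will provide an assessment of the severity of each AE by recording a severity rating". The scale has three grades, with severe at the top. The same section says that severity, "which is a description of the intensity of manifestation of the AE, is distinct from" seriousness. Section 9.5.4.6 covers an AE that turns serious: "If, during follow-up, any nonserious AE worsens and eventually meets the criteria for an SAE, that AE should be recorded as a new SAE". It does not say which start date the new record takes. Section 9.5.4.1 gives, among its examples of AEs, new disease after consent, "including any change in severity or frequency of pre-existing disease".

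**Classification (SAP 5.1.1.4.2, Table 5-20).** A treatment-emergent event must first satisfy "Treatment start date ≤ event start date ≤ treatment end date + 1". It must then either be a term never reported before treatment start or meet the worsening condition: "The same term is reported before the treatment start date and the term increases in severity on or after the treatment start date". That increase is measured as "Event severity > maximum severity of same term reported before the treatment start date". A second category, on-therapy, uses dates only: "Treatment start date ≤ event start date ≤ treatment end date + 30".

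**The concern.** The worsening condition is there to pick up events that were present at the first dose and deteriorated on drug. It recognises one kind of deterioration, a higher grade. The protocol treats seriousness as a separate attribute and gives conversion to an SAE its own recording rule, but Table 5-20 has no matching criterion. A patient with a moderate AE in screening who is hospitalised for it on treatment, still graded moderate, has a new SAE record and no treatment-emergent event.

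The date requirement adds a dependency. The worsening condition works only if the worsening sits in a record with an on-treatment start date, and the visible text does not guarantee that for every kind of worsening.

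Long-term safety is a secondary objective, and the open-label phase that all patients enter has no control arm. A classification loss of this kind removes events and adds none, and no comparison group offsets it.

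**Working it through.** This is a question about a classification rule. The documents state no figure for it, so there is none to reproduce. The check writes the two Table 5-20 definitions as logical rules and runs them on the ways a screening-onset AE could be recorded.

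**Inputs**
- Treatment start = day 0; treatment end = day 364 (52 × 7).
- Treatment-emergent (SAP Table 5-20): 0 ≤ start ≤ 364 + 1 = 365, and either no pre-dose report of the term or grade > highest pre-dose grade of that term.
- On-therapy (SAP Table 5-20): 0 ≤ start ≤ 364 + 30 = 394.
- Grades (Protocol 9.5.4.3): mild 1, moderate 2, severe 3.
- Recording rule (Protocol 9.5.4.6): a nonserious AE that becomes serious gets a new SAE record. I read follow-up in that sentence as follow-up of the event, not the post-treatment Follow-up Period.

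**Results**

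| Case | How it is recorded | Date test | Grade test | Treatment-emergent | On-therapy |
|---|---|---|---|---|---|
| A | Original record kept (day −10), grade raised | −10 < 0, fails | not reached | No | No |
| B | New record day 60, mild to moderate | passes | 2 > 1 | Yes | Yes |
| C | Original record kept (day −10), turned serious (not as 9.5.4.6 instructs) | fails | not reached | No | No |
| D | New SAE record day 60, moderate to severe | passes | 3 > 2 | Yes | Yes |
| E | New SAE record day 60, moderate and still moderate | passes | 2 > 2 false | **No** | Yes |
| F | New SAE record day 60, already severe before dosing | passes | 3 > 3 false | **No** | Yes |
| G | New SAE record carrying the day −10 onset, mild to severe | fails | not reached | No | No |
| H | New SAE record day 60 under a different term | passes | no earlier report | Yes | Yes |

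**Reading the table**
1. B and D show that the worsening condition works when a higher-grade record is opened on treatment.
2. E and F need no assumption about how the eCRF handles grade changes. The site follows 9.5.4.6, dates the record at worsening, and the event still fails because only grade is tested. In F no higher grade exists.
3. A and G fail both definitions, but only if sites keep the original record for a grade change (A) or carry the original onset date onto the new SAE record (G). The public text does not settle either.
4. C arises only if 9.5.4.6 is not followed.

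**Size.** Only AEs that begin in screening are exposed. That window is at most 3 weeks against 52 on treatment: 3 / (3 + 52) = 3/55 = 5.5% of the combined time. The documents give no rate of screening AEs and no share that worsen, so the number of patients affected cannot be computed.

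**The case against.** The strongest reply is that the plan already handles worsening. Table 5-20 has an explicit condition for it, and 9.5.4.6 requires a new SAE record, which passes the date test if dated at worsening and is treatment-emergent if the grade rose. That stands, and it confines the demonstrated gap to cases E and F.

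Second, the on-therapy category has no severity test and catches E and F. That also stands. These events are not lost from every possible table, and the public text does not show which term the SAE tables use. It does not make them treatment-emergent.

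Third, much of the surrounding text is not public. Protocol 9.5.4.2, the protocol's AE analysis sections and SAP Tables 5-21 to 5-26 are not shown, and newly emergent adverse event is listed as an abbreviation whose definition cannot be seen. Any of these, or the eCRF instructions, may say how a grade increase is recorded. Protocol 9.5.4.1 also points towards recording a change in severity as an event in its own right, although its wording refers to pre-existing disease. So a reader might infer from the single severity rating in 9.5.4.3 that a nonserious grade increase is always missed. The documents do not support that. Nor do they show that raising a grade after dosing would also raise the pre-dose maximum: Table 5-20 refers to severity reported before treatment start.

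Fourth, the pool is small. Inclusion criterion 7 bars clinically significant findings before the first dose, and exclusion criterion 2 bars any watery stools in the week before Day 1, which limits pre-dose diarrhea, the drug's main known AE. This is a fair argument about size. It does not change how the rule classifies E and F.

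**Conclusion.** The gap holds in a limited form. As written, Table 5-20 does not count as treatment-emergent a screening-onset AE that becomes serious on treatment at an unchanged or already severe grade, even when the site follows 9.5.4.6. Such an event is on-therapy only. Cases A and G, which would fail both definitions, remain possible but depend on eCRF rules that are not visible.

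A reader might go further and conclude that on-treatment worsening is in fact undercounted in the long-term safety tables. The supportable statement is that it can be undercounted in treatment-emergent summaries, since neither the table specifications nor the eCRF instructions can be seen.

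A reader might also attach a number. Assuming that 5% to 15% of 800 patients have a screening-onset AE still present at the first dose, and that 10% to 25% of those worsen, gives 800 × 0.05 × 0.10 = 4 to 800 × 0.15 × 0.25 = 30 patients (0.5% to 3.75%). All four shares are assumptions, and the product counts every worsening as lost although cases B and D are counted correctly. It is not an estimate of the effect. The number is unknown and probably small.

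The primary ADA endpoint is untouched. The change is worth making because the flaw is in a stated rule, concerns events that became serious, and is cheap to correct.

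**What to change.** **SAP Table 5-20, second condition.** Count a term reported before treatment start if, on or after treatment start, it increases in severity or becomes serious. In operational terms: the event's severity exceeds the pre-dose maximum for the term, or the event is serious and no pre-dose report of the term was serious. Cases E and F then become treatment-emergent.

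**Protocol 9.5.4.6 and eCRF instructions.** State that the new SAE record starts on the date of worsening; case G then passes the date test and is classified as case D. Confirm that a post-dose grade increase in a nonserious AE opens a new record with its own start date and grade; case A then becomes case B. If the eCRF instructions already say this, a cross-reference from the SAP is enough.

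**Cost.** One SAP sentence and one eCRF instruction. Expect a few more AE rows and a slightly higher treatment-emergent rate. Participant counts are not inflated, because SAP Table 5-3 counts each participant once per category.
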